5 STUDY DESIGN

5.1 OVERALL DESIGN

We plan to conduct a quasi-experimental, single-arm pilot/feasibility trial of a VAP diagnostic stewardship bundle in the MM Critical Care Medicine Unit (CCMU) and Cardiac Care Unit (CCU). This is a population-based rather than individual intervention. Both the CCMU and CCU will designate team leaders (one faculty member, fellow, and unit nurse), who will be instructed on study design and rationale, to disseminate study information and education in concert with study PI to colleagues through use of infographics and powerpoint-based sessions.

The study intervention will consist of interventions at all 3 phases of the diagnostic testing pathway (see Section 7 for full details). The bundle's first two interventions (ordering & collection phase interventions) will be implemented at the onset of the study period. The final bundled intervention (reporting phase) will be implemented 6 months after study onset (see Study Timeline (section 1.2)).

5.2 SCIENTIFIC RATIONALE FOR STUDY DESIGN

The majority of antimicrobial stewardship interventions are system-based interventions, operationalized at the level of individual hospital, hospital units or outpatient clinics. Thus, quasi-experimental pre/post study designs are a widely utilized and validated approach for studies of large-scale antimicrobial stewardship interventions.

5.3 JUSTIFICATION FOR INTERVENTION

VAP is overdiagnosed and overtreated, resulting in ICU antibiotic overuse which degrades patient care. Novel antimicrobial stewardship approaches to combat ICU antimicrobial overuse are required.

5.4 END-OF-STUDY DEFINITION

The study will conclude after 1 year of intervention operationalization (February 2023).

6 STUDY POPULATION

6.1 INCLUSION CRITERIA

This pilot/feasibility trial will occur within the Michigan Medicine Cardiac Care Unit (CCU, 7D) and the Michigan Medicine Critical Care Medicine Unit (CCMU, 6D). This study will not be screening or enrolling individual patients, but rather instituting system-based interventions in the diagnostic testing workflow that providers engage with as part of routine clinical care. Study subjects in this trial are therefore all patients hospitalized in the aforementioned Michigan Medicine ICUs during the study period requiring invasive mechanical ventilation, as well as healthcare providers providing care to said patients in the aforementioned ICUs during the study period.

6.2 EXCLUSION CRITERIA

For the study intervention requiring performance of bronchoalveolar lavage rather than endotracheal aspirate for respiratory culture collection, the following are exclusion criteria for performance of bronchoalveolar lavage: INR>2, platelet count <50, gross blood in endotracheal secretions, P/F ratio<80, major lung surgery in prior 30 days. There are no exclusion criteria for study interventions at the ordering and reporting phases of the diagnostic testing pathway.

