- *Current state:* There is wide variability in ICU practice patterns for acquiring respiratory specimens. 60% of respiratory cultures in ICUs at our institutional are obtained from proximal lung samples, most frequently via endotracheal aspiration (ETA). ETAs are convenient to acquire, but growth of microorganisms from ETA adds little to the diagnostic specificity of VAP, as pathogenic organisms often colonize endotracheal material within hours of intubation.⁶⁰⁻⁶² ETA samples demonstrate low concordance with organisms isolated from the lung itself in both animal models and human studies.^{62,63} Distal lung sampling, via bronchoalveolar lavage (BAL), offers the advantage of directly sampling the alveolar space and can be performed without bronchoscopic guidance by Respiratory Therapists at Michigan Medicine for equivalent supply and labor cost to ETAs. In multiple randomized controlled trials, use of BAL rather than ETA for respiratory collection in suspected VAP has been associated with lower rates of antibiotic use, without increased rates of mortality or ventilator-dependence.⁶⁴⁻⁶⁷

3. Reporting (postanalytic) phase:

- *Current state:* Physicians routinely utilize the number and proportion of white blood cells recovered from bodily fluid to determine the significant of positive culture results (for example, this is considered standard of care in ascites fluid, pleural fluid and urine). Using this data from clinical specimens helps providers to differentiate infection from contamination when a clinical culture grows bacteria. For example, if a patient grows bacteria from a urine specimen, but the patient’s urine has few to no white blood cells present, it virtually assures that the bacteria recovered is not causing a clinical infection. In a VAP enriched population of 851 ICU patients, our collaborators have demonstrated that BAL neutrophil percentage <50% has a negative predictive value of 92% for ruling out VAP.⁶⁸ Autopsy studies have similarly shown that BAL neutrophil percentage <50% approaches a sensitivity of 100% in ruling out infection.⁶⁹ Despite this, alveolar neutrophilia has never been adopted for diagnostic stewardship purposes. Similarly, all respiratory cultures include

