Respiratory culture result reporting	Respiratory culture results automatically released in EHR only for BAL samples with a PMN% of >50% . Respiratory culture results for BAL samples with PMN% <50% released upon direct primary team request to Clinical Microbiology Lab.	Modification to Clinical Microbiology Laboratory workflows.	The following prompt was provided for suppressed respiratory culture results: 
 • "Culture results suppressed due to <50% PMNs seen in BAL, which has a sensitivity of 95% for diagnosis of bacterial pneumonia in non-neutropenic patients. Please call the Microbiology Laboratory within 7 days if identification/antimicrobial susceptibility testing are needed."

CDS=clinical decision support; EHR=electronic health record; CXR=chest X-ray; CT=computed tomography; BAL=bronchoalveolar lavage; PMN%=percentage of polymorphonuclear neutrophils observes on BAL cell count/differential.

1. Ordering (preanalytic) phase:

- Study intervention: In participating ICUs, all providers who order respiratory cultures will be automatically routed to a custom study order set within the electronic medical record. This order set will require providers to select a valid clinical indication for respiratory culture performance (worsening hypoxia, new infiltrate on chest imaging, purulent sputum production), but will not include aforementioned scenarios in which respiratory culture collection is *not* indicated (fever or leukocytosis without features localizing infection to the respiratory tract, changes in secretions that are *not* purulent, transient respiratory decompensations that rapidly improve without supportive care).

2. Collection (analytic) phase:

- Study intervention: In participating ICUs, all providers who order respiratory cultures will be automatically routed to a custom study order set within the electronic medical record. This order set will require physician or RT-guided BAL for respiratory collection rather than endotracheal aspiration for mechanically-ventilated patients, provided there are no specific exclusion criteria for individual patients (see Section 4.1 for specific patient exclusion criteria). Importantly, Respiratory Therapists are trained in the use of BAL for respiratory collection and routinely perform these procedures hundreds of times a year for precisely

this purpose. Performance of BAL is considered standard of care by national and international VAP expert guidelines.^{9,10}

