3. Reporting (postanalytic) phase:

- *Study intervention:* In participating ICUs, all providers who order respiratory cultures will be automatically routed to a custom study order set within the electronic medical record. This order set will require performance of BAL for all patients without exclusion criteria (see Section 4.1) in whom respiratory cultures are ordered. The order set will include not only an order for respiratory culture from BAL (performed by the Michigan Medicine Clinical Microbiology lab), but also a BAL cell count and differential. The Michigan Medicine Clinical Microbiology lab will work up all respiratory cultures according to current practices, but will not release the culture reports to providers for samples in which the BAL neutrophil % is less than 50%. When providers examine the culture result in the electronic medical record, an automated message will indicate that the BAL neutrophil % is low on the sample, making pneumonia exceedingly unlikely. Providers will be informed in this automated message that they can call the Michigan Medicine Clinical Microbiology lab and manually request release of the results if they feel it is indicated.

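### Low-neutrophil BAL cultures are withheld by default from neutropenic patients too, although the prompt's own accuracy figure leaves them out

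*Combined protocol and SAP*

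**What the plan says.** - **Scope.** Section 6.1 takes in every invasively ventilated patient in the two ICUs. Section 6.2 lists contraindications to BAL ("INR>2, platelet count <50, gross blood in endotracheal secretions, P/F ratio<80, major lung surgery in prior 30 days") and then says: "There are no exclusion criteria for study interventions at the ordering and reporting phases of the diagnostic testing pathway". No neutrophil count appears in either place.
- **Release rule.** In the Section 7.1.1 table, culture results go out automatically only when the BAL PMN percentage exceeds 50%. Below 50% they are "released upon direct primary team request to Clinical Microbiology Lab".
- **Prompt.** The message on a suppressed result attributes the suppression to a PMN percentage under 50%, "which has a sensitivity of 95% for diagnosis of bacterial pneumonia in non-neutropenic patients". It continues: "Please call the Microbiology Laboratory within 7 days if identification/antimicrobial susceptibility testing are needed". The word non-neutropenic in this prompt is the documents' only mention of neutropenia.
- **Narrative.** The reporting-phase text of Section 7.1.1 says the "lab will work up all respiratory cultures according to current practices, but will not release the culture reports to providers" when the BAL neutrophil percentage is low. It adds that "an automated message will indicate that the BAL neutrophil % is low on the sample, making pneumonia exceedingly unlikely", and that providers may call to have the result released.
- **Evidence.** Section 2.2 cites a "VAP enriched population of 851 ICU patients, our collaborators have demonstrated that BAL neutrophil percentage <50% has a negative predictive value of 92" per cent. It also cites autopsy studies, attaching a sensitivity approaching 100% to the same low result.

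**The concern.** The reporting rule rests on the premise, argued in Section 2.2, that few white cells in a sample make infection unlikely. That premise needs a patient who can mount a neutrophil response. The prompt concedes as much by restricting its figure, but the rule that triggers the prompt carries no such restriction. For a neutropenic patient the default is to withhold a result without any evidence in the protocol that a low PMN percentage argues against pneumonia. Release then depends on a clinician noticing the qualifier and calling the laboratory.

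Section 3.1.1 treats prompt cultures and receipt of susceptibility results as central to managing VAP, and delay to effective therapy as a determinant of outcome. Safety is the trial's primary objective. The Section 9.4.1 safety measures are ICU-level mortality, ventilator-associated events and ventilation duration, and Section 9.4.2 stratifies only by ICU and implementation phase. Neither would isolate a problem in this group.

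A smaller matter is that the prompt gives a sensitivity for a negative finding. Clinicians read this text when deciding whether to ask for release, so the figure should be the right one.

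**Working it through.** **1. Does any text exempt neutropenic patients?**

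| Place | What it does for a neutropenic patient |
|---|---|
| 6.1 | Includes them |
| 6.2, BAL contraindications | No neutrophil criterion; the platelet limit may keep some from having a BAL |
| 6.2, reporting phase | No exclusions |
| 7.1.1 table and narrative | Withholds if PMN is below 50%, whoever the patient is |
| 7.1.1 prompt | States that its accuracy figure does not cover them |

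No exemption exists, and no accuracy data for this group are given.

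**2. How much exposure?** The reporting phase starts 6 months after onset (Section 5.1), and the study ends after 1 year of intervention (Section 5.4). That leaves 12 − 6 = 6 months. Within those months only BAL recipients with a PMN percentage below 50% are affected. The number of them who are neutropenic is not given, so it cannot be computed.

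**3. Can the 95% belong to the low result?** The 95% comes with no counts, specificity or prevalence, so it cannot be rebuilt. It can be tested against the 92% negative predictive value (NPV) in Section 2.2.

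Read literally, 95% of pneumonia cases have a low PMN percentage. At prevalence p, the NPV is greatest when every patient without pneumonia also has a low result:

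maximum NPV = (1 − p) / [(1 − p) + 0.95p]

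Using the prevalences that Section 2.2 assumes elsewhere (10%, and 20–30%):

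- p = 0.10: 0.90 / 0.995 = 90.5%
- p = 0.20: 0.80 / 0.990 = 80.8%
- p = 0.30: 0.70 / 0.985 = 71.1%

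Setting the maximum equal to 0.92 gives p = 0.08 / (0.08 + 0.874) = 8.4%. Above that prevalence the literal reading cannot coexist with a 92% NPV, and the 92% comes from a population described as enriched for VAP.

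Now assign the 95% to a PMN percentage of 50% or more. With specificity s, an NPV of 92% implies

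p = 0.08s / (0.08s + 0.92 × 0.05)

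The documents give no specificity. Over an assumed range of 0.4 to 0.8, p runs from 0.032 / 0.078 = 41% to 0.064 / 0.110 = 58%, which is plausible for an enriched population. This is the sensible reading.

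**4. What the two figures mean.**

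- Sensitivity 95%: 1 − 0.95 = 5% of non-neutropenic pneumonia cases fall below the cut-off.
- NPV 92%: 1 − 0.92 = 8% of low results, about 1 in 12 (1 / 0.08 = 12.5), were VAP in the enriched population.

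These are different quantities, and the second depends on prevalence. Neither measures performance in neutropenic patients: the first excludes them, and the second comes from a population whose neutrophil status is not stated.

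**The case against.** The strongest defence is that the design leaves the judgement with the people best placed to make it. The treating team knows the blood neutrophil count; a release rule driven by the BAL differential does not. The prompt shows the qualifier on the suppressed result itself and then says whom to call. Release needs no approval, the narrative says all cultures are worked up, and Section 3.1.3 says antibiotic prescribing is not prohibited. The data and safety monitoring board meets every two months with a halting rule. All of this stands and limits the harm. It does not remove the gap, because the default still runs against the patients for whom the rule has no stated support, and the board's measures are aggregate.

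Several stronger readings are tempting but not supported:

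- *That neutropenic patients are denied results or treatment.* They are not; the default is reversed by a call.
- *That a low PMN percentage is shown to mislead in neutropenia.* The documents give no accuracy for that group in either direction.
- *That clinicians will see an uncaveated message.* The narrative only paraphrases the prompt; the table gives its wording, caveat included.
- *That the sensitivity wording causes harm.* The intended meaning is clear, and no direction of harm follows from it. It is a minor correction and adds nothing to the seriousness of the missing exemption.
- *That identification and susceptibility testing are not done unless requested.* The prompt's last sentence can be read so, but the narrative has all cultures worked up. The point needs confirming.

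**Conclusion.** The concern holds as a gap in scope that should be fixed: the suppression rule covers all patients, its quoted accuracy covers only those without neutropenia, and nothing in the protocol bridges the two. This conclusion follows from the text and needs no assumed inputs. Its clinical size is unknown. Exposure is bounded by the 6-month reporting phase, by the need for a BAL and a low PMN percentage, and by release on request.

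The sensitivity wording is a separate, minor error, occurring in both the prompt and Section 2.2. That the literal reading fails rests on taking the 92% NPV at face value and on prevalence in its source population exceeding 8.4%.

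**What to change.** 1. **Main change.** In Section 6.2 and the Section 7.1.1 table, release BAL culture results by default for neutropenic patients. Define neutropenia by an absolute neutrophil count cut-off, chosen by the study team and applied to the latest blood count, with the flag raised in the order set or at laboratory release.
2. **Minor correction.** In the prompt and in Section 2.2, assign the sensitivity to a PMN percentage of 50% or more. Alternatively, quote the 92% NPV for the low result and name its VAP-enriched source. Keep the non-neutropenic limit and the 7-day call instruction in the prompt.
3. **Before editing the prompt's last sentence,** have the laboratory confirm whether identification and susceptibility testing are already complete or are done on request. New wording should not presume the answer.

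**Cost.** Slightly fewer cultures are suppressed, and one check is added. Section 6.2 already uses INR and platelet count to decide who may have a BAL, so consulting blood results is not new to the protocol. A blood-count check at laboratory release would be new.

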7 STUDY INTERVENTION(S)

7.1 STUDY INTERVENTION(S) ADMINISTRATION

7.1.1 Study Intervention Description

This study's VAP diagnostic stewardship bundle will include interventions that occur at discrete phases in the diagnostic testing pathway: 1) the *preanalytic phase*, in which tests are ordered; 2) the *analytic*

phase, in which diagnostic specimens are collected and laboratory tests are performed; and 3) the postanalytic phase.

Trial Interventions

Diagnostic Testing Phase	Intervention	Implementation method	Details
Respiratory culture ordering	CDS tool requiring providers to select a valid indication for respiratory culture performance : 
 • New radiographic infiltrate on CXR or chest CT • Purulent endotracheal secretions • Worsening PEEP and/or FiO2 	Interruptive EHR alert triggered upon respiratory culture order, tagged to custom CDS order set.	The following prompts were given to providers using the CDS order set: 
 • Fever or leukocytosis without aforementioned culture indications is unlikely to indicate pneumonia. • Radiographic infiltrates consistent with atelectasis or pulmonary edema do not require respiratory cultures. • Purulent secretions are different than thickened or increased nonpurulent secretions (the latter do not require cultures). • Transient worsening of PEEP or FiO2 that rapidly improves is unlikely to indicate pneumonia
Respiratory culture collection	CDS tool requiring providers to use non-bronchoscopic BAL (performed by respiratory therapists) when no contraindications present. All BAL specimens automatically sent for quantitative respiratory culture & cell count/differential .	Interruptive EHR alert triggered upon respiratory culture order, tagged to custom CDS order set	Contraindications to BAL were as follows: 
 • major lung surgery in prior 30 days • gross blood in endotracheal secretions • INR>2 • platelet count <50k • P/F ratio <80. Consideration of bronchoscopy was recommended for sampling upper lobe infiltrates.
Respiratory culture result reporting	Respiratory culture results automatically released in EHR only for BAL samples with a PMN% of >50% . Respiratory culture results for BAL samples with PMN% <50% released upon direct primary team request to Clinical Microbiology Lab.	Modification to Clinical Microbiology Laboratory workflows.	The following prompt was provided for suppressed respiratory culture results: 
 • "Culture results suppressed due to <50% PMNs seen in BAL, which has a sensitivity of 95% for diagnosis of bacterial pneumonia in non-neutropenic patients. Please call the Microbiology Laboratory within 7 days if identification/antimicrobial susceptibility testing are needed."

CDS=clinical decision support; EHR=electronic health record; CXR=chest X-ray; CT=computed tomography; BAL=bronchoalveolar lavage; PMN%=percentage of polymorphonuclear neutrophils observes on BAL cell count/differential.

1. Ordering (preanalytic) phase:

- Study intervention: In participating ICUs, all providers who order respiratory cultures will be automatically routed to a custom study order set within the electronic medical record. This order set will require providers to select a valid clinical indication for respiratory culture performance (worsening hypoxia, new infiltrate on chest imaging, purulent sputum production), but will not include aforementioned scenarios in which respiratory culture collection is *not* indicated (fever or leukocytosis without features localizing infection to the respiratory tract, changes in secretions that are *not* purulent, transient respiratory decompensations that rapidly improve without supportive care).

2. Collection (analytic) phase:

- Study intervention: In participating ICUs, all providers who order respiratory cultures will be automatically routed to a custom study order set within the electronic medical record. This order set will require physician or RT-guided BAL for respiratory collection rather than endotracheal aspiration for mechanically-ventilated patients, provided there are no specific exclusion criteria for individual patients (see Section 4.1 for specific patient exclusion criteria). Importantly, Respiratory Therapists are trained in the use of BAL for respiratory collection and routinely perform these procedures hundreds of times a year for precisely

this purpose. Performance of BAL is considered standard of care by national and international VAP expert guidelines.^{9,10}

3. Reporting (postanalytic) phase:

- *Study intervention:* In participating ICUs, all providers who order respiratory cultures will be automatically routed to a custom study order set within the electronic medical record. This order set will require performance of BAL for all patients without exclusion criteria (see Section 4.1) in whom respiratory cultures are ordered. The order set will include not only an order for respiratory culture from BAL (performed by the Michigan Medicine Clinical Microbiology lab), but also a BAL cell count and differential. The Michigan Medicine Clinical Microbiology lab will work up all respiratory cultures according to current practices, but will not release the culture reports to providers for samples in which the BAL neutrophil % is less than 50%. When providers examine the culture result in the electronic medical record, an automated message will indicate that the BAL neutrophil % is low on the sample, making pneumonia exceedingly unlikely. Providers will be informed in this automated message that they can call the Michigan Medicine Clinical Microbiology lab and manually request release of the results if they feel it is indicated.

7.2 FIDELITY

7.2.1 Provider Training

Providers will be counseled on CDST use during bimonthly educational sessions over a 3-month trial rollout period and via subsequent monthly email reminders thereafter. Each ICU will designate a nursing and physician champion to facilitate implementation.

